6.5.1 Procedures to be performed per visit

6.5.1.1 Scrutiny visit

- Signature of informed consent: refers to the signing of the written informed consent document. See 10.3 Consent
- General and ophthalmological medical history: refers to the technical, clinical, and legal document that chronologically records the patient's health conditions, medical procedures, and other procedures performed on the patient. It includes a comprehensive ophthalmological history and examination to determine the patient's eligibility, i.e., evaluation of both eyes and ocular adnexa, slit-lamp examination of the ocular surface and anterior segment, and fundoscopy . If the patient is recruited from the study center's established office, the existing medical history may be used; only one update is required.
- Laboratory sampling: see 6.4.3.9 Laboratory tests.
- Pregnancy test: see 6.4.3.8 Pregnancy test.
- Eligibility criteria: Refers to the PI's review, which verifies that the subject can be included in the study if they meet the inclusion criteria and do not meet the exclusion criteria. See 6.2 Eligibility criteria
- Intraocular pressure: see 6.4.3.5 Intraocular pressure
- Visual capacity: see 6.4.3.1 Visual capacity
- TRL: see 6.4.3.7 Tear film break-up time
- Ocular surface stains: see Ocular surface stains
- Vital signs: see 6.4.3.6 Vital signs

6.5.1.2 Baseline visit

- Laboratory Test Review: Refers to the PI's review and analysis of the BHc , QS, and PFH results. See 6.4.3.9 Laboratory tests.
- Eligibility criteria: The laboratory results will determine the subject's profile for inclusion or exclusion.
- Assignment: This refers to determining the intervention the patient will follow during the study. This will be done according to section 7. Methods. Intervention allocation . This assignment will be done at the baseline visit (day 0) and will be accompanied by the indication to begin the treatment period the following day (day 1).
- Delivery of intervention: Refers to the delivery of the investigational product to the study patient by the research center. This will be carried out in accordance with sections 6.3.1 Treatments administeredand 6.3.4.1 Delivery and receipt.
- Variable Assessment: Data from the assessment of the variables listed below may be taken from the scrutiny visit, as long as it is not taken more than 7 days prior to this visit. It is the IP's prerogative to decide whether to use the information from the scrutiny visit or repeat the assessments during this visit.
 - Intraocular pressure
 - Visual capacity
 - TRL
 - Ocular surface stains
 - Vital signs
- Eye comfort index: see 6.4.3.2 Eye comfort index
- Delivery of the subject's diary: Refers to the delivery by the IP to the subject of the subject's diary instrument.

6.5.1.3 Visit 1

- Adherence assessment: refers to the assessment carried out by the IP in accordance with section 6.3.2.1 Procedure for monitoring adherence
- Adverse events: see 6.4.3.4 Presence of adverse events
- Intraocular pressure: see 6.4.3.5 Intraocular pressure
- Visual capacity: see 6.4.3.1 Visual capacity
- TRL: see 6.4.3.7 Tear film break-up time
- Ocular surface stains: see Ocular surface stains
- Vital signs: see 6.4.3.6 Vital signs
- Submission of the subject's diary: see 6.5.1.2 Baseline visit
- Return/Review of Subject Diary: Refers to the subject handing over the subject diary to the PI. The PI will review the diary to ensure it is complete correctly, assess post-instillation symptoms , and record the applications.
- Subject Continuance Assessment: Refers to the PI's determination of the subject's desire to continue participating in the study.

6.5.1.4 Final Visit

- Laboratory sampling: see 6.4.3.9 Laboratory tests
- Pregnancy test: see 6.4.3.8 Pregnancy test
- Return of intervention: see 6.5.1.3 Visit 1.
- Adherence assessment: refers to the assessment carried out by the IP in accordance with section
- Adverse events: see 6.4.3.4 Presence of adverse events
- Intraocular pressure: see 6.4.3.5 Intraocular pressure
- Visual capacity: see 6.4.3.1 Visual capacity
- TRL: see 6.4.3.7 Tear film break-up time
- Ocular surface stains: see Ocular surface stains
- Vital signs: see 6.4.3.6 Vital signs
- Eye comfort index: see 6.4.3.2 Eye comfort index
- Subject diary return/evaluation: see 6.5.1.3 Visit 1.
- Return/evaluation of the quality questionnaire: refers to the submission of the quality questionnaire to the IP by the subject.

6.5.1.5 Safety call

- Adverse events: see 6.4.3.4 Presence of adverse events
- Laboratory test review: see 6.5.1.2 Baseline visit

6.5.2 Study diagram

An enrollment time of 30 days is estimated for the entire sample.

[figure not shown]

Figure 3Study diagram

6.6 Sample size

A total size of 32 subjects is estimated, distributed in 2 intervention groups. [16 subjects (16 eyes) per group]

6.6.1 Sample size calculation

There are no references on the calculation of the sample size in phase I studies, and the formulation of Humylub Ofteno® has not reported any adverse events in its periodic safety reports. Therefore, it was considered appropriate to base the calculations on previous phase I studies conducted by Laboratories . Sophia , SA de CV [45, 46, 47, 48].

The calculation was based on the adverse event presentation reported by Christ T., in a randomized, single-blind, parallel-group controlled clinical trial evaluating the efficacy and tolerability of a 5% dexamphenol ophthalmic gel versus a 5% panthenol ointment in 48 subjects with corneal erosion, UV-induced keratoconjunctivitis, or similar conditions. The intervention consisted of applying 1 cm of the gel and ointment for 4 and 3 days, respectively.[49]

The percentage of good tolerance reported with the gel was 25%, so it is expected that no more than 10% of subjects will report poor tolerance with the formulation proposed in this protocol.

The sample size was calculated using the formula for proportions

$$n = p (1 - p) \left(\frac{Z_{1-\alpha} + Z_{1-\beta}}{p - p_0 - \delta} \right)^2$$

With a statistical confidence of 95% corresponding to type I error, equal to 1.96, with a power of 90%, corresponding to type II error, equal to 0.84.

According to the previous calculation, the result is 26 subjects, which was increased by 20% to account for probable losses. The total required sample size is **32 subjects** . Therefore, each group will consist of 16 subjects, each of whom will contribute an eye to the analysis.

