For adverse event reporting, all eyes of participants randomized to an intervention group after the baseline visit will be considered. Results will be expressed as the number of cases (eyes).

The final results report will be displayed in tables or graphs, as appropriate.

The investigational drug will be considered safe and tolerable when there are no clinical or statistical differences in all primary outcome variables compared to its comparators.

Subjects with an adherence rate greater than 60% will be included in the statistical analysis to meet the study objective, based on the subject's diary. However, even if the subject's diary indicates adherence greater than 60%, if the adherence calculated by weight is less than 30%, the subject will not be included. The minimum dose necessary to obtain a pharmacological effect (lubricant/1 gel application per day) and the presence of adverse events (exposure) were considered sufficient to meet the overall design objective, in accordance with the pharmacological characteristics of the investigational product.

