Return of intervention	X			
Adherence assessment		X	X	
Adverse events		X	X	X
Intraocular pressure	X	1 x	X	X
Visual Ability	X	1 x	X	X
TRL	X	1 x	X	X
Ocular surface stains	X	1 x	X	X
Vitals	X	1 x	X	X
Eye Comfort Index		X		X
Subject Diary Delivery		X	X	
Return / Evaluation of the subject's Journal			X	X
Return and Evaluation of the Quality Questionnaire				X
Subject continuity assessment			X	

^a The counting visit may be up to 10 days prior to the baseline, if it exceeds these the subject will not be able to enter.

^b These criteria shall be supplemented by the results of laboratory examinations and those collected during the screening visit.

^c An indication will be given to start the application the next day.

¹ They can be taken from the scrutiny visit, as long as no more than 10 days have elapsed, it is the prerogative of the PI to measure them again at the baseline visit.

Sample Size

An estimated 32 evaluable subjects are divided, divided into two groups [16 subjects (16 eyes) exposed per group].

[figure not shown]

Figure 1. Suggested work scheme.

Sample Size Calculation

There are no references to sample size calculation in phase I studies, and the formulation of Humylub Ofteno® has not reported adverse events in its periodic safety reports. For this reason, it was considered pertinent to base it on the calculations of previous phase I studies, carried out by Laboratorios Sophia, S.A. de C.V., with formulations of ocular lubricants in the same pharmaceutical presentation.

The calculation was in accordance with the presentation of adverse events reported by Christ T (1994), in a randomized, single-blind, parallel-group controlled clinical trial where the efficacy and tolerance of a 5% dexpanthenol ophthalmic gel versus a 5% panthenol ointment in 48 subjects with corneal erosion was evaluated. keratoconjunctivitis from UV radiation or similar conditions. The intervention consisted of the application of 1 cm of the gel and ointment for 4 and 3 days, respectively. [1][2]

The percentage of good tolerance that was presented with the gel was 25%, so it is expected that no more than 10% of the subjects report a bad tolerance with the formulation proposed in this protocol.

The sample size was calculated using the formula for proportions.[3]

$$n = p(1 - p) \left(\frac{z_{1-\alpha} + z_{1-\beta}}{p - p_0 - \delta} \right)^2$$

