With a statistical confidence of 95% that corresponds to type I error, equal to 1.96, with a power of 90%, corresponding to type II error, equal to 0.84.

According to the previous calculation, the result is 26 subjects, which was increased by 20% due to the probable losses. The total sample size required is **32 subjects**. So each group will be made up of 16 subjects, who will provide an eye for the analysis.

Analysis Plan [4]

Outcome Variables

Safety primary outcome variables:

- Incidence of Adverse Events.

Primary outcome variables of tolerability:

- ICO score.

Secondary Outcome Variables:

- Tear film rupture time (LRT).
- Vital signs: HR, RF and SAP.
- Posterior segment.
- Quality questionnaire.
- Intraocular pressure.
- Visual capacity.
- Laboratory Tests: BHc, QS, PFH.
- Ocular surface stains.

Table 2. Operational Definition of the Variables

Chondroitin Sulfate 0.18%/Sodium Hyaluronate 0.2%

Variable	Conceptual Definition	Operational Definition	Measurement Type	Normal value	Statistical test
Adverse events (AEs).	Any undesirable medical event that may occur in an investigational subject during the clinical research stage of a drug or vaccine but does not necessarily have a causal relationship with it. ⁴	Adverse events manifested during the conduct of the study will be collected using the CRF.	
 - Continuous quantitative. - Categorical qualitative. 	
 - Frequency: Subjects with AEs/Total number of exposed subjects. - Intensity: 0= Mild 1= Moderate 2= Severe - Causality: 0= Improbably related. 1= Probable or possibly related. 2= Related 	
 - Pearson's square chi or Fisher's exact. - U for Mann-Whitney.
Changes in Intraocular Pressure (IOP).	Tonometry is the objective measurement of IOP, based primarily on the force required to flatten the cornea or the degree of corneal indentation produced by a fixed force.	Goldmann tonometry. 3 samples will be taken, which will be recorded in the clinical file and the average will be recorded in the CRF.	
 - Continuous quantitative. 	
 - 11-21 mmHg. 	
 - U for Mann-Whitney. - Wilcoxon Ranges.

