- Intra-group difference: McNemar test. This is applied to 2x2 contingency tables with a dichotomous feature, with pairs of paired subjects, to determine if the marginal frequencies of row and column are equal (marginal homogeneity).
- Difference between groups: Pearson's Chi-square (χ^2) test or Fisher's exact test at expected values less than 5.

The level of difference to consider significance (p) will be an alpha (α) of 0.05 or less.

Chondroitin Sulfate 0.18%/Sodium Hyaluronate 0.2%

For the reporting of adverse events, all eyes of those participants who were randomly assigned to an intervention group after PI instillation (ITT) will be considered.

The final report of the results will be shown in tables or graphs, as appropriate.

Those subjects who meet a minimum adherence of 60% will be included in the statistical analysis to meet the objective of the study, taken from the subject's diary. However, even if the subject's adherence is greater than 60% per diary, if the adherence calculated by weight is less than 30%, the subject will not be included.

The investigational drug will be considered safe and tolerable when there are no clinical and statistical differences in all primary outcome variables, with respect to its comparator (Artelac® Nighttime Gel).

Table 3. Triangulation of concepts

Variable Type	Variable	A1	B1	B2	C1	D1	E1	E2	E3	E4	E5	E6	E7	E8
Background														
A1	Demographic			DT										
Basal														
B1	Medical History		DT			T								
B2	Comprehensive ophthalmological evaluation		DT	DT		TB			TB		B	B		T
Safety														
C1	Incidence of AD			TB	TB		TB	TB	TB		TB	TB	TB	TB
Tolerability														
D1	ICO			DB			DB							
Secondary outcome														
E1	TRL			DB		TB		DB						
E2	Vitals			DB		TB			B					

Chondroitin Sulfate 0.18%/Sodium Hyaluronate 0.2%

E3	Posterior segment	DB	TB	B
E4	Quality Questionnaire			TB
E5	PIO	DB	TB	B
E6	Visual Ability	DB	TB	B
E7	Laboratory tests	DB	TB	B
E8	Ocular surface stains	TB	TB	TB

D. Descriptive Statistics; T, 2x2 contingency table; B, Bivariate Analysis; M, Multivariate Analysis.

Changes

1. First version of the document, no changes apply.

Author of the document

Ph.D. in Cs. [name].

Biostatistics.

Clinical Operations.

Laboratorios Sophia, S.A. de C.V.

[name]

[name]

References

<https://doi.org/10.1007/BF03163747>.

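### The 90% power claim rests on the z-value for 80%, an n of 26 that the printed inputs do not give, and a one-sample formula split over two arms

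*Protocol*

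**What the plan says.** Protocol 6.6.1 and the SAP's Sample Size Calculation give the same derivation. The formula is n = p(1 − p)[(Z₁₋α + Z₁₋β)/(p − p₀ − δ)]², with 1.96 for the type I error and "with a power of 90%, corresponding to type II error, equal to 0.84". Two rates are offered. One comes from a published trial of a different gel: "The percentage of good tolerance reported with the gel was 25" per cent. The other is the expectation that "no more than 10% of subjects will report poor tolerance with the formulation proposed in this protocol". Neither rate is labelled p or p₀, and δ has no value in either document.

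The protocol then says "the result is 26 subjects, which was increased by 20% to account for probable losses", which makes 32 in total and 16 per group. The SAP's Sample Size section describes the same number differently: "An estimated 32 evaluable subjects are divided".

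The analysis compares the two arms. Adverse events are tested by chi-square, or in the SAP by Fisher's "exact test at expected values less than 5". Protocol 8.3.1 sets the conclusion: "The investigational drug will be considered safe and tolerable when there are no clinical or statistical differences" in all primary outcome variables against the comparator. The SAP repeats this rule. The ICO score is also primary; the SAP lists it under "Primary outcome variables of tolerability".

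**The concern.** The stated power and its z-value do not match, and the reader cannot rebuild the 26. The formula also answers a different question from the one the trial asks. It has a single p(1 − p) term and a fixed p₀, so it sizes one group against a constant, whereas the trial compares two randomised arms.

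The two quoted rates describe opposite outcomes (good tolerance of one product, poor tolerance of another), so as written they cannot both enter one formula.

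The stake is how a null result will be read. Absence of a statistical difference is part of the success criterion, so low power favours a favourable conclusion. Someone who believes the trial had 90% power will take a non-significant result as much stronger evidence of similarity than it is. A formula for proportions also says nothing about the ICO score.

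**Working it through.** **Inputs.** From protocol 6.6.1: z-values 1.96 and 0.84, rates 0.25 and 0.10, n = 26, 20% for losses, 32 in total. From 8.3.1: alpha 0.05. Not given: δ, which rate is p or p₀, and any adverse event rate for the comparator.

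**1. Power label.** Φ(0.84) = 0.7995, so 0.84 is 80% power. For 90%, z = 1.2816. Scaling the sponsor's 26 within its own formula: 26 × [(1.96 + 1.2816)/2.80]² = 34.85, that is 35 before losses.

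**2. Reproducing 26.** All rows use the one-sample formula.

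| Reading | Calculation | n |
|---|---|---|
| p = 0.10, p₀ = 0.25, δ = 0 | 0.09 × (2.80/0.15)² | 31.4 |
| p = 0.25, p₀ = 0.10, δ = 0 | 0.1875 × (2.80/0.15)² | 65.3 |
| 25% good read as 75% not good, p = 0.10 | 0.09 × (2.80/0.65)² | 1.7 |
| the same, variance at 0.25 × 0.75 | 0.1875 × (2.80/0.65)² | 3.5 |
| p = 0.10, p₀ = 0.25, δ = 0.015 | 0.09 × (2.80/0.165)² | 25.9 |
| p = 0.10, p₀ = 0.25, δ = 0, one-sided 1.645 | 0.09 × (2.485/0.15)² | 24.7 |

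The only close readings need a δ that is stated nowhere, or a one-sided 1.645 that contradicts the printed 1.96. Both use 0.84, so both are at 80% power. With 1.2816, the δ = 0.015 reading gives 34.7.

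**3. Losses.** 26 × 1.2 = 31.2, rounded up to 32, so this step reproduces. But 32 × 0.8 = 25.6, and keeping 26 after 20% losses needs 26/0.8 = 32.5, that is 33. Nor can the 32 be all evaluable if it already includes an allowance for losses.

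**4. What two arms of 16 can show.** The arm rates here are assumptions. Two-sided power at alpha 0.05, by full enumeration of both binomials:

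| Assumed rates | Per arm | Fisher | SAP rule (Fisher if an expected count is below 5) | Uncorrected chi-square |
|---|---|---|---|---|
| 10% vs 25% | 16 | 9.7% | 10.4% | 19.7% |
| 10% vs 25% | 13 | 6.3% | 6.3% | 14.3% |
| 10% vs 75% | 16 | 96.4% | – | – |
| 10% vs 75% | 13 | 93.5% | – | – |

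With 10% in one arm, 90% power at 16 per arm needs about 63% (SAP rule) or 68% (Fisher) in the other. With no events in one arm, Fisher reaches significance only at 5/16 in the other (p = 0.043); 4/16 gives p = 0.10.

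**5. Precision.** At 2/16 in each arm the Wald half-width is 1.96 × √(2 × 0.125 × 0.875/16) = 0.229. The Newcombe 95% interval is −0.252 to 0.252.

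**The case against.** The best defence is that this is a Phase I trial labelled exploratory, with specific and secondary objectives that are descriptive, so no formal power is needed. That is a good reason to keep 32 subjects. It is not a reason to keep a stated 90%, least of all beside a rule that uses absence of difference as evidence.

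Several narrower points are fair:

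- With p = 0.10, p₀ = 0.25 and δ = 0 the formula gives 31.4, which rounds up to 32, the enrolled total. But the documents say the formula gave 26 and that 32 includes losses.
- The formula's subscript is Z₁₋α, so a one-sided 1.645 may be where the number came from. That does not fit the printed 1.96, or 90%.
- Good tolerance may be a slip for poor tolerance, since the text says the calculation was based on adverse events. The result would then be 31.4 or 65.3, still not 26.
- The decision rule requires no clinical difference as well as no statistical one, so non-significance is not the whole criterion. No clinical threshold is given, however.
- Adverse event reporting counts all randomised participants, so the 13-per-arm figures may not apply to that outcome.
- The two-arm powers depend on assumed rates and range widely. They are also powers to detect a difference, not to show similarity. The SAP mentions non-inferiority criteria but gives no margin, so power for that cannot be calculated.
- Sizing on one of two primary variables is common in exploratory work, so the ICO point is secondary.

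None of this restores the 26 or the 90%.

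**Conclusion.** The concern holds and should be fixed. Three defects need no assumption about event rates: 0.84 is 79.95% power, not 90%; the 26 does not follow from the printed inputs; and a one-sample n was divided between two arms that are then compared with each other. The conflict over whether 32 is before or after losses is smaller but real.

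The size of the power shortfall does depend on assumed rates. At 10% versus 25%, power with 16 per arm is about 10% under the SAP's rule and at most 20%. It reaches 90% only if the rates are very far apart, roughly 10% versus 63% to 68%. What the documents do not support is any claim that the between-arm comparison has 90% power.

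**What to change.** In protocol 6.6.1 and the SAP's sample size sections:

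- Keep 32 subjects and say that this is a pragmatic size for an exploratory Phase I trial.
- Delete the 90% power claim. Relabelling it 80% would leave the missing inputs and the one-sample formula in place.
- If the formula stays, print p, p₀ and δ for one and the same outcome, match the z-value to its subscript, and state that it is a one-sample calculation that does not size the between-arm comparison or the ICO score.
- State what 16 per arm gives for the between-arm adverse event difference: a 95% interval of about ±25 percentage points (Newcombe) at 2/16 versus 2/16. Placed beside the decision rule, this shows how little a non-significant result excludes; the rule itself is left unchanged.
- Label any power figure as conditional on assumed rates and give its range.
- Say whether 32 is the number enrolled or the number evaluable. If 26 evaluable is the aim, note that 20% losses from 32 leave 25.6.

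The cost is wording in two documents. No subjects, visits or analyses are added. The sponsor gives up the stated 90%.

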6.7 Recruitment

It is recommended that during the development of this research protocol, the principal investigator request approval from the Research Ethics Committee and the Research Committee, as well as authorization from the relevant regulatory body, to publish or disseminate in mass media the invitation to participate in the study to those individuals who meet the eligibility criteria.

It is possible to discuss with other health professionals the opportunity for healthy subjects to be evaluated by an ophthalmologist at no cost, as well as undergo office examinations that will allow for a more precise determination of their clinical ocular status by participating in a clinical research protocol sponsored by Laboratorios Sophia SA de CV.

7. Methods. Intervention allocation

7.1 Generating the assignment sequence

Two strata will be used for the intervention groups, which will be balanced for each research center. The allocation will be 1:1. Data will be generated through a validated electronic system from an external provider, previously evaluated and authorized by Laboratorios Sophia SA de CV. Information regarding this provider will be found in the study's master folder.

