6.1 Study center

This study will be conducted in properly equipped and registered ophthalmology offices. Depending on the sponsor's needs, these offices may be private or public, attached to a hospital or clinic, or independent.

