6.1.1 Organization of the center

Each study center will have a principal investigator (PI). The PI is the ophthalmology specialist leading the clinical study.

The PI is responsible for forming a multidisciplinary research team to execute the clinical study according to the protocol, under his or her scientific guidance. The PI is responsible for designing the organization of his or her center and selecting the personnel who will perform these functions. However, the minimum organization of the research team requested by the sponsor requires the following: a sub-investigator , study coordinator, and pharmacist. (See **Figure 2Minimum organization of the center.**)

Any person designated by the PI as responsible for monitoring the study (coinvestigator, sub-investigator, nurse, etc.) or for a specific role in the study (pharmacist, administrative assistant, study coordinator, etc.) must be listed on the “Delegation of Responsibilities” form.

[figure not shown]

Figure 2Minimum organization of the center

The "Delegation of Responsibilities" and the "Center Organizational Chart" must be submitted to the sponsor before the start of the study and updated if the members or their responsibilities change.

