6.4.3.6 Vital signs

The vital signs to be assessed (HR, RR and SBP) may be measured by an assistant duly designated in the center's organization and the delegation of responsibilities. The technique to be used for HR and RR will be counting repetitions in one minute by direct auscultation with a stethoscope.

SBP should be measured after 5 minutes of rest on the left arm. The instrument may be manual or automatic, as the PI deems appropriate. All measurements must be performed under equal conditions. Three measurements will be taken, with a minimum interval of 5 minutes between measurements, and recorded in the patient record. The average will also be recorded on the grade and the CRF.

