9.4.1 Pre-study audit

The research centers included in the study will be subject to a pre-study visit prior to center selection, where they will be verified to meet the minimum requirements indicated by the sponsor.

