The data will be collected and sorted in an Excel spreadsheet (Microsoft® Office). The data will then be exported to the SPSS program platform. The variables will be categorized according to their nature (see [Table 2](#)).

Study participants will be identified by a number and their initials.

The initials of the study subject will be obtained starting with the first letter of the name, followed by the first letter of the first surname and the first letter of the second surname, obtaining a maximum of three letters, in case the person has two names or compound surname, the first letter will always be used.

Example:

To. [name]	B. [name]
to. Initials: AMC	b. Initials: JDO

Once the subject has been selected, they will be assigned a number with which they will be identified throughout the study. This code will be made up of eight numbers in the following order from left to right:

- Three digits of the molecule under study according to the name by the sponsor.
- Two digits corresponding to the research centre number.
- Three digits of the number following their inclusion assigned to the research centre.

The results of the continuous quantitative variables will be presented in measures of central tendency: mean, standard deviation and ranges, see [Table 2](#).

The Kolmogorov-Smirnov and Shapiro Wilk test will be performed to determine the type of distribution of the data (normality) in the results obtained in each study group. [5]

The statistical analysis of the continuous quantitative variables to find significant differences (p) will be as follows:

- Intra-group analysis: will be determined by Wilcoxon's rank test, for quantitative variables. [6]
- Inter-group analysis: Differences between groups will be analyzed using the Mann-Whitney U statistic.

The level of difference to consider significance will be an alpha (α) of 0.05 or less. A 95% CI will be considered for the non-inferiority criteria.

The result of the nominal and ordinal qualitative variables will be presented in frequencies, proportions and percentages, see [Table 2](#).

The statistical analysis to identify significant differences in the qualitative variables will be carried out by creating 2x2 contingency tables and will be carried out as follows:

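### Arms are balanced within centre but every between-arm test pools centres; if several centres enrol and differ, some sensitivity is lost, which favours a finding of no difference

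*Protocol*

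**What the plan says.** Protocol 7.1 describes the allocation: "Two strata will be used for the intervention groups, which will be balanced for each research center". It continues: "The allocation will be 1:1". The two strata are not named, and the phrase may simply mean the two arms, but balance within centre is explicit.

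The protocol allows for several centres without fixing a number. Section 6.1 says "This study will be conducted in properly equipped and registered ophthalmology offices", and section 9.4.1 says "The research centers included in the study will be subject to a pre-study visit prior to center selection". Section 6.1.1 gives each centre its own principal investigator. Section 6.6 sets the size: "A total size of 32 subjects is estimated, distributed in 2 intervention groups", 16 per arm.

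The between-arm tests are as follows.
- Protocol 8.3.1, quantitative variables: Kruskal-Wallis, with Student's t also named.
- SAP Methods of Analysis, quantitative variables: "Differences between groups will be analyzed using the Mann-Whitney U statistic".
- Both documents, qualitative variables: Pearson chi-square or Fisher's exact test on 2x2 tables.

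None of these includes centre. SAP Table 3 has a code for multivariate analysis in its legend, but no cell uses it. Protocol 8.3.2 plans no further analyses.

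Both documents treat the product as safe and tolerable if no clinical or statistical difference from the comparator appears in the primary outcomes, which are adverse events and the eye comfort index.

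**The concern.** Balancing the arms within each centre removes centre differences from the comparison of arms. A test that ignores centre still counts those differences as random error. Its standard error is then too large, it rejects a true null less than 5% of the time, and it misses real differences more often.

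In a superiority trial this would cost only the sponsor. Here the favourable conclusion follows from not finding a difference, so an insensitive test makes that conclusion easier to reach for a reason unrelated to the product.

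Centres could plausibly differ. Staining and break-up time are judged by eye, and investigators elicit and rate adverse events. For blood pressure, protocol 6.4.3.6 says "The instrument may be manual or automatic, as the PI deems appropriate".

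**Working it through.** **The plan's own figure.** Protocol 6.6.1 raises 26 subjects by 20%: 26 × 1.2 = 31.2, rounded up to 32, or 16 per arm. The calculation has no centre component. How 26 was obtained does not affect this point.

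**Inputs from the documents.** 16 per arm; 1:1 balance within centre; alpha 0.05, taken as two-sided because the alternative hypothesis is a different profile.

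**Assumptions, not in the documents.** 2 or 4 equal centres; centre share of variance (ICC) from 0 to 0.5; normal outcome; true difference of 1 within-centre SD.

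**Formula.** Let σw² be the within-centre and σc² the between-centre variance, with ICC = σc² / (σw² + σc²). Under within-centre balance the arm difference has true variance 2σw²/n. The pooled test acts as if it were 2σw² / [n(1 − ICC)]. In that approximation 16 per arm behaves like 16(1 − ICC): 14.4 at ICC 0.1, 11.2 at 0.3 and 8.0 at 0.5.

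**Hand check of type I error at ICC 0.3.** The ratio σc²/σw² is 0.3/0.7 = 0.429. With K centres the average realised spread is (K − 1)/K of this: 0.214 for two centres and 0.321 for four. The effective critical value is 1.96 × √1.214 = 2.16 (two-sided 3.1%) or 1.96 × √1.321 = 2.25 (2.4%). Simulation gives 3.3% and 2.5%.

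**Simulation, 40,000 trials per setting.** The rank model regresses the overall ranks on arm and centre. Van Elteren is the rank test stratified by centre.

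| Centres | ICC | Pooled type I | Pooled power | Van Elteren power | Rank model power | Rank model minus pooled |
|---|---|---|---|---|---|---|
| 2 | 0 | 4.7% | 75.3% | 74.4% | 76.3% | 1.0 |
| 2 | 0.1 | 4.3% | 73.0% | 74.0% | 76.0% | 3.0 |
| 2 | 0.3 | 3.3% | 67.4% | 74.0% | 75.6% | 8.2 |
| 2 | 0.5 | 2.6% | 59.3% | 74.0% | 75.4% | 16.1 |
| 4 | 0 | 4.8% | 75.3% | 72.3% | 76.2% | 0.9 |
| 4 | 0.1 | 3.8% | 72.2% | 72.1% | 76.0% | 3.8 |
| 4 | 0.3 | 2.5% | 63.4% | 71.9% | 74.9% | 11.5 |
| 4 | 0.5 | 1.5% | 51.4% | 72.4% | 74.8% | 23.4 |

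The rank model's type I error stays at 5.0 to 5.2% in these rows. Repeat runs move the differences by up to about a point. The 1-point gap at ICC 0 reflects the slightly conservative normal approximation in the pooled test and not centre; it also appears with a single centre.

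**Adverse events at the 10% and 25% used for planning, 16 per arm, 20,000 trials.** Pooled Fisher against an exact test stratified by centre:
- two centres, same rates in each: power 9.8% against 10.0%;
- four centres, same rates in each: 9.9% against 8.9%;
- two centres with rates 5% and 15% in one arm, 15% and 35% in the other: 9.3% against 9.7%.

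A clear gap needs very unlike centres. With base rates of 5% and 45%, type I error is 0.8% pooled and 2.0% stratified.

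**The case against.** The strongest objection is that the size rests on two quantities the documents do not give. Nothing in them suggests that centre explains 30 to 50% of the variance. Eligibility narrows the population to healthy adults aged 18 to 45 with vision, pressure, vital signs and laboratory values in range. At a share of 10% the loss is only 3 to 4 points. This stands: the larger figures are the upper part of an assumed range, not an expectation.

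A second objection is that the likeliest centre differences lie outside the decision rule. A reader might infer that subjective grading of staining and break-up time, or the choice of blood-pressure instrument, drives the safety conclusion. The documents do not support this. Those outcomes are secondary, and the rule covers primary outcomes only. SAP Table 2 defines staining, break-up time, intraocular pressure and vision as changes, in which stable centre shifts largely cancel. Section 6.4.3.6 also requires blood-pressure measurements to be made under equal conditions.

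Among the primary outcomes, adverse events gain almost nothing from stratification at the planning rates. That leaves the comfort index. Subjects answer it themselves, with help only in understanding a question, but SAP Table 2 lists it as a score and not as a change, so centre differences in level need not cancel.

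Third, the pooled test remains valid in the sense that its type I error does not exceed 5%, and the trial is exploratory. That is true, but validity under the null gives little comfort when non-significance is the favourable result.

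**Conclusion.** The point holds as a conditional, modest one. Allocation uses centre and the analysis does not. If more than one centre enrols and centres differ, the pooled tests are conservative and less sensitive, in the direction that favours the product. For 2 to 4 centres and a 1 SD difference, the loss against a centre-adjusted rank model is about 1 point with no centre effect, 3 to 4 at a 10% share, 8 to 12 at 30% and 16 to 23 at 50%. With one centre there is no centre-related loss. The figures assume normal outcomes and equal centres. The comfort index is the main primary outcome concerned.

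A reader might also infer that a large loss of power has been shown, or that adjusting for centre would make a null result trustworthy. Neither follows. The centre share is unknown, and the larger weakness is reading non-significance at 16 per arm as similarity. For 10% against 25% adverse events, power is only about 10% with Fisher's test (about 19% by normal approximation) even without centre differences. Centre adjustment does not cure that.

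**What to change.** In protocol 8.3.1 and SAP Methods of Analysis, state that if more than one centre enrols, the comfort index and the other quantitative variables will be compared between arms with a rank-based model containing arm and centre. Keep the pooled Mann-Whitney test as a sensitivity analysis, and as the main analysis if only one centre enrols.

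The rank model is preferable to van Elteren here. With four centres of eight subjects and no centre effect, van Elteren gives up 75.3 − 72.3 = 3.0 points against the pooled test, and it gains nothing at a 10% share (72.1% against 72.2%).

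An exact test stratified by centre for adverse events is optional. In protocol 7.1, name centre explicitly as the stratification factor and remove the ambiguity about two strata.

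The cost is small. No new data are needed, because the subject code in protocol 6.2.4 already carries the centre number. There is slightly more analysis work, and residual degrees of freedom fall from 30 to 29 with two centres or 27 with four.
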